⁹ We propose to document the prevalence of inconsistent and missing data in a descriptives table presented as an appendix in our final impact report. Along with our presentation of sensitivity analyses, we will present tables that present the prevalence of unit and item missing (which result from nonresponse) as well as inconsistent, unreliable, and invalid data for both treatment and control samples. Regarding inconsistencies specifically, for each sexual behavior variable included in our model specifications (which could therefore influence the constitution of the analytic sample) we will include the following: sample size (the number of observations prior to recoding of inconsistencies) and the number of observations that are inconsistent over-time. If paper questionnaires lead to internally inconsistent data, we will also report on this.

¹⁰ A note on missing values: Stata provides a series of missing value codes that allow us to "flag" missing data according to why they are missing. Data that are missing due to unit nonresponse (a questionnaire was not completed) are coded using the "system missing" value (.). All other types of missing data are coded using "extended missing" values (e.g., ".a", ".b").

as missing.¹¹ PRG flags the following cases as unreliable: a) the same response option is chosen for all multiple choice questions; b) responses alternate between only two response options; or c) responses alternate systematically, starting with one response option, alternating through all options in order until exhausted then beginning again (in the same or in reverse order). If other response patterns are observed over the course of the evaluation, they will be added to PRG's list of unreliable response patterns.

Data for cases that are deemed unreliable are treated as *unit missing* and excluded from benchmark analyses. However, sensitivity analyses that include the unreliable data will be conducted and results will be reported in an appendix of the report.

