- iv.* **Identify and flag inconsistencies in reporting of sexual behaviors:** The fourth step in the data review process is to inspect the data and identify inconsistencies in sexual behavior outcome data. With repeated measures of sexual behaviors, two primary types of inconsistencies may occur – internal inconsistencies and over-time inconsistencies.¹⁴ Internal inconsistencies refer to discrepancies in responses (to related questions) in the same survey administration. For instance, a respondent might say that they have not had sex in the past three months, but then indicates that they used condoms three of the times they had sex in the past three months. Over-time inconsistencies refer to instances in which lifetime reported behaviors decline or are completely recanted over time. For example, at baseline a respondent might say that they have had vaginal sex in their life, but on a subsequent administration of the survey say that they have never had vaginal sex.

In order to minimize internal inconsistencies in our primary outcomes, we have skip patterns in the paper questionnaire – if participants indicate they have not had a particular type of sex they are instructed to skip out of more specific questions related to that type of sex; and if they state they have never had sexual contact, they are instructed to skip out of questions asking about how many sexual partners they have had over certain periods of time. However, it is possible for participants to provide responses to questions that they should not have answered or that do not make sense given their responses to previous questions. If and when such inconsistencies are observed, the participant’s responses to the two or more items where inconsistencies are noted are recoded to system missing and will not be used in our primary outcome analysis.¹⁵

To address over-time inconsistencies, a research analyst examines all variables that are used to construct primary outcome measures, as well as any variables that may be used to logically impute values for primary outcome measures. If over-time inconsistencies are identified, both the baseline and follow-up values are flagged as inconsistent over time and recoded to missing (coded as “.k.”). Data that are recoded to missing are treated according to our missing data approach. Briefly, our benchmark approach is to adjust missing baseline data and include in analysis; we exclude observations with missing outcome data from analysis.

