¹⁴ Inconsistencies can occur for a number of reasons including social desirability bias and memory or recall issues on the part of the respondent and misunderstanding on the part of either the respondent or interviewer (Alexander et al 1993; Clarke, Fiebig, and Gertham 2008; Del Boca and Noll 2000; Harris et al 2008; Schroeder et al 2003; Schwarz and Oyserman 2001). These issues are especially common in self-reports of sexual behaviors where questions are of a sensitive nature and often respondents are asked to indicate the frequency and/or recency of behaviors over differing lengths of time (e.g., 30 days, 3 months, 6 months).

¹⁵ In the online questionnaire, automatic skip patterns have been built into the instrument. Because of this, internal inconsistencies cannot exist in data collected through the online instrument.

- v. **Missing data approach:** Assuming that our study design and procedures are sound, missing data pose perhaps the greatest threat to the internal validity of our RCT study and the ITT framework (Puma et al. 2009; Moher et al., 2010).¹⁶ Randomization at the point of offer allows us to make causal statements about the effect of that offer because treatment and comparison samples are equal in expectation. For the ITT framework to remain internally valid, however, the treatment and comparison groups must remain equal in expectation at the point of analysis. When the analytic sample is diminished by attrition or non-response, non-random differences (i.e., self-selecting) between the treatment and comparison groups may be introduced into the sample and estimates of program impacts may become biased. Although there is no consensus on how to resolve this, practical guidance on how to address and mitigate the problems associated with missing data have been published in education (Puma et al., 2009).

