Our six-step decision process for addressing this problem, as detailed below, is informed by this guidance. These steps articulate how we will deal with missing outcome or baseline/covariate data (that is variables outlined in the *Model specification and covariates* section and are necessary for the estimation of impacts). The benchmark approach that we have selected aims to mitigate the introduction of bias into our impact and maximize the use of available data by adjusting missing baseline/covariate data. To test the robustness of this approach, and to verify these findings, we will report comparative findings using sensitivity analyses that also employ an alternative method which includes no adjustment (as outlined in step 6).

1. Using data cleaning procedures outlined in the *Data cleaning* section, identify inconsistent, outlying, unreliable, and invalid data in any analytic (i.e., outcome, baseline, or covariate) variables, recode inconsistent and invalid data as missing, and flag unreliable and outlier data for analysis.¹⁷
2. Report prevalence of unit and item missingness (which result from nonresponse) as well as inconsistent, unreliable, and invalid data for both treatment and control samples.¹⁸
3. Determine if logical imputations are possible for any analytic variables that may have missing values (due to nonresponse) and logically impute where this is the case. We will not logically impute where the missing values are previously inconsistent, unreliable, or invalid.
4. Determine if any individuals who are in the randomized sample (for each outcome) do not have outcome data at the 10th grade follow-up time point. If this is the case, our proposed benchmark approach is to use case deletion, as we feel it is the most straightforward and prudent approach for missing follow-up data recommended in Puma et al. (2009). These cases will be deleted from the analytic sample and attrition statistics will be reported.

¹⁶ Puma, M.J., Olsen, R.B., Bell, S.H., Price, C. (2009). What to Do When Data Are Missing in Group Randomized Controlled Trials. (NCEE 2009-0049). Washington, DC: National Center for Education Evaluation and Regional Assistance, Institute of Education Sciences, U.S. Department of Education. Moher, D. et al. (2010). CONSORT 2010 Explanation and Elaboration: Updated Guidelines for Reporting Parallel Group Randomised Trials. *BMJ* 2010;340:c869.

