$$Attrition_{student} = 1 - \left(\frac{Assessed_{student}}{Base_{student}} \right)$$

where:

$Attrition_{student}$ - the proportion of students enrolled in the study who did not complete a 10th grade follow-up questionnaire

$Base_{student}$ - the number of students enrolled into the study

$Assessed_{student}$ - the number of students who completed a 10th grade follow-up questionnaire

Differential attrition will be calculated using the following formulas:

$$Attrition_{student\ C} = 1 - \left(\frac{Assessed_{student\ C}}{Base_{student\ C}} \right)$$

$$Attrition_{student\ T} = 1 - \left(\frac{Assessed_{student\ T}}{Base_{student\ T}} \right)$$

$$Differential\ Attrition_{t-c} = abs(Attrition_{student\ T} - Attrition_{student\ C})$$

Where:

$Attrition_{t-c}$ - the absolute difference between the proportion of treatment group students who did not complete a 10th grade follow-up questionnaire and the proportion of control group students who did not complete a 10th grade questionnaire

$Attrition_{student\ C}$ - the proportion of students enrolled in the study and randomly assigned to the control group who did not complete a 10th grade follow-up questionnaire

$Base_{student\ C}$ - the number of students enrolled into the study and randomly assigned to the control group

$Assessed_{student\ C}$ - the number of students randomly assigned to the control group who completed a 10th grade follow-up questionnaire

$Attrition_{student\ T}$ - the proportion of students enrolled in the study and randomly assigned to the treatment group who did not complete a 10th grade follow-up questionnaire

$Base_{student\ T}$ - the number of students enrolled into the study and randomly assigned to the treatment group

$Assessed_{student\ T}$ - the number of students randomly assigned to the treatment group who completed a 10th grade follow-up questionnaire

Overall and differential attrition will be reported in the findings section of our final impact report.

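### Does deleting students who answer Yes at baseline and No at tenth grade distort the sexual-initiation result?

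*Combined protocol and SAP*

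**What the plan says.** Section 4c.iv defines the problem narrowly: "Over-time inconsistencies refer to instances in which lifetime reported behaviors decline or are completely recanted over time". When this occurs, "both the baseline and follow-up values are flagged as inconsistent over time and recoded to missing". The same section adds that "we exclude observations with missing outcome data from analysis". Section 4c.v, step 3, closes the route back: "We will not logically impute where the missing values are previously inconsistent, unreliable, or invalid". Step 4 says of students without outcome data: "These cases will be deleted from the analytic sample and attrition statistics will be reported".

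Initiation is a single lifetime Yes/No item (section 4a). Times having sex and number of partners are three-month counts, and a lifetime answer of never is coded as zero.

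On reporting, footnote 9 in section 4c promises, for each sexual behavior variable in the models, the sample size before recoding and "the number of observations that are inconsistent over-time". Section 4c.v, step 2, promises the prevalence of inconsistent data in both arms. The attrition formula in section 4f.ii counts as assessed "the number of students who completed a 10th grade follow-up questionnaire".

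The sensitivity analyses in section 4f.iv cover covariates, baseline adjustment, unreliable cases, outliers, late responders and model form. Section 3d adds the exclusion of phone respondents. None restores over-time inconsistent reports; unreliable cases are those with patterned answers, which is a different category.

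**The concern.** The rule works in one direction. It cannot remove a student who moves from No to Yes, so every deleted record carries a reported outcome of No. Membership of the analytic sample then depends on an answer given after randomization. Footnote 14 says of the causes of inconsistency: "These issues are especially common in self-reports of sexual behaviors where questions are of a sensitive nature". The Evaluation Abstract adds that some students will probably know their assignment before baseline. If PGC changed willingness to admit sexual experience, deletion would differ by arm, and one would fear a false program effect on a primary outcome with no alternative run to expose it.

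Secondary outputs also seem exposed. The baseline-equivalence table uses the post-deletion sample (section 4d, footnote 25). The run without covariates may or may not keep the baseline outcome. Footnote 30 allows a switch from OLS to logit, in which baseline Yes predicts the outcome perfectly. For the two counts, the plan does not say whether a recanted lifetime item makes the three-month value missing.

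**Working it through.** **Inputs.** From the documents: the rule above, the model in section 4f.i (treatment plus baseline outcome), 1:1 allocation, and the Cox index in section 4d. They give no recanting or initiation rates, so there is no plan figure to reproduce. Assumed: 20% Yes at baseline; among baseline-No students, 20% initiate in control and 15% in PGC (or 20% in both for the null); recanting among baseline-Yes students of 10% to 30%. Expected cell proportions are used; school dummies and demographics are left out.

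**1. What is deleted.** Of the four answer pairs (No/No, No/Yes, Yes/No, Yes/Yes), only Yes/No. Retained baseline-Yes students all have outcome 1.

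**2. Adjusted OLS.** The treatment coefficient is a weighted mean of the within-stratum differences, with weight w = n_T × n_C / (n_T + n_C).
- Baseline-No: w = 0.8 × 0.8 / 1.6 = 0.4, untouched by the rule.
- Baseline-Yes: difference 1 − 1 = 0, whatever the recanting rates.

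Under the null both differences are zero, so the estimate is 0.000. This holds at 10% in control against 15%, 20% or 25% in PGC.

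**3. True effect, equal recanting r.** The estimate is −0.05 × 0.4 / [0.4 + 0.1(1 − r)].

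| r | Estimate |
|---|---|
| 0 (all kept) | −0.05 × 0.4/0.500 = −0.0400 |
| 10% | −0.05 × 0.4/0.490 = −0.0408 |
| 15% | −0.05 × 0.4/0.485 = −0.0412 |
| 30% | −0.05 × 0.4/0.470 = −0.0426 |

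The change is 2% to 6%.

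**4. Alternative codings, 10% v 25% recanting.**
- Deletion: the baseline-Yes weight is 0.18 × 0.15/0.33 = 0.0818, giving −0.05 × 0.4/0.4818 = −0.0415. Null: 0.000.
- Yes at either wave: −0.0400. Null: 0.000.
- As reported: the baseline-Yes difference is 0.75 − 0.90 = −0.15, giving 0.8 × (−0.05) + 0.2 × (−0.15) = −0.070. Null: −0.030.

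**5. Secondary outputs, null, 10% v 25%.**
- Baseline Yes among the retained: 0.18/0.98 = 18.4% v 0.15/0.95 = 15.8%. Cox index = ln(0.75/0.90)/1.65 = −0.110.
- No-covariate run that also drops the baseline outcome: (0.15 + 0.16)/0.95 − (0.18 + 0.16)/0.98 = −0.021. If the baseline outcome stays: 0.000.
- Deleted but counted as assessed: 0.20 × 10% = 2% v 0.20 × 25% = 5% of respondents.
- With 5% or 10% Yes at baseline, 20% v 30% recanting and 15% new initiation, the no-covariate shift is −0.004 or −0.008. The standard error of an unadjusted difference at 800 per arm and 20% prevalence is √(2 × 0.2 × 0.8/800) = 0.020.

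**6. Logit.** With 15% recanting in both arms and the true effect above, logit and OLS give p = 0.034 v 0.034 at an assumed n = 1,300. At n = 1,600, the enrollment expected in the Evaluation Abstract with no attrition, they give 0.019 v 0.019. The risk difference is −0.050 when the logit is read on baseline-No students only. Averaged over all retained students it is −0.041 for logit, Firth logit and OLS alike.

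**7. Times having sex, if a recanted lifetime item does make the count missing.** Further assumptions: half of baseline-Yes students have a baseline count of 0 and half of 5; at tenth grade 40% of them report zero and the rest average 6; 20% of baseline-No students are active, with mean 3. With no true effect:
- 15% v 40% of zero-reporters recanting: deletion +0.051, as reported 0.
- 10% v 25% recanting unrelated to the count: deletion −0.042, as reported −0.20 × 0.15 × 3.6 = −0.108.

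Neither reading is uniformly less biased.

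**The case for a change.** The best case for a change is consistency. The plan reruns the analysis without outliers because it cannot know whether extreme values are true. The same doubt applies to recanted answers, yet they get no second run. Counts by arm would let a reader rebuild crude initiation proportions but not the adjusted estimate. For two of three primary outcomes, two analysts could code the same student differently. Step 4 of section 4c.v promises attrition statistics for deleted cases, while the formula in section 4f.ii treats the same students as assessed.

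Part of this stands. No planned run restores these students, and the count rule is not explicit. But the two obvious extra runs for initiation add little: coding Yes at either wave barely moves the estimate, and as-reported coding brings in the reporting error that the rule keeps out. The baseline-equivalence table would reveal differential deletion rather than hide it, which is what that diagnostic is for. Perfect prediction in the logit is not caused by the rule. It arises whenever a lifetime item is answered consistently, and section 4f.iv already names Firth logit. Footnote 14 speaks of causes of inconsistency in general and goes on to frequency and recency questions; it gives no rate of recanting a lifetime Yes.

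For the counts there is a natural reading. Section 4c.iv examines all variables that feed the primary outcomes. Once a lifetime item is set to missing it no longer says never, so the zero coding loses its basis, and step 3 bars imputation. Questionnaire attrition and item-level loss are two different quantities, and both are to be reported.

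**Conclusion.** No change to the plan is needed. The rule is one-directional and is not tested by any planned run, but the benchmark for initiation is sound. The adjusted estimate stays at 0.000 under the null even when recanting differs by arm, because the retained baseline-Yes students cannot differ between arms. A true effect is overstated by 2% to 6% under equal recanting of 10% to 30%, and by about 4% (−0.0415 v −0.0400) at 10% v 25%.

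The visible effects, a Cox index of −0.110 and a no-covariate shift of −0.021, need recanting that differs markedly by arm. The second also needs the baseline outcome to be dropped from that run. Both would be read beside inconsistency counts by arm.

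The rest is detail that analysts can fill in: the treatment of recanted items in the counts (effect of unknown size and direction), whether the no-covariate run keeps the baseline outcome, and how deletions are labeled beside attrition. The Table 3 row in Appendix A that mentions only baseline values for these items is a clerical omission, since section 4c.iv states the full rule. A run coding initiation as Yes if reported at either wave would be a harmless optional addition.

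All rates are assumptions, and the calculation leaves out school and demographic terms.
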